## **2. Glossary and Abbreviations**

|      |  |
|------|--|
| IGM  | Idiopathic Granulomatous mastitis          |
| MRI  | Magnetic resonance imaging                 |
| CNGM | Cystic neutrophilic granulomatous mastitis |

### 3. Rationale

Idiopathic granulomatous mastitis (IGM) is a benign inflammatory condition of the breast first described by Kessler and Wolloch in 1972 [1]. The etiology of IGM is largely unknown due to its rare occurrence with an estimated prevalence of 2.4 per 100,000 women aged 20-40 years [2, 3]. Valid data on the prevalence of IGM in Europe are lacking. However, the incidence in the low-income countries appears to be higher compared to western Europe [4], [5], [6]. Since only case reports and small case series of IGM have been so far reported in the literature, our knowledge on risk factors, clinical course of disease, therapeutic management, and clinical outcomes is very limited. Based on the published cases, IGM is considered to predominantly occur in women of childbearing age, mostly parous and more frequently of non-white ethnicity [2, 7-10].

The local symptoms of IGM are mostly severe, lasting up to many weeks or months, causing strong pain and often mimicking inflammatory breast cancer (Fig 1). Diagnosis can be confirmed only by histological evaluation, usually using core needle biopsy. The patients commonly develop recurrent breast abscesses, which do not improve on antibacterial medication and often require repeat incisions or drainages. The degree of suffering of IGM patients is therefore very high.

IGM needs to be differentiated from granulomatous inflammation of the breast that can appear in duct ectasia, as a reaction to foreign material, or in association with specific infections (e.g., mycobacteria, fungi, parasites) as well as in the course of systemic granulomatous diseases such as sarcoidosis. Further, cystic neutrophilic granulomatous mastitis (CNGM) was recently described as a specific form of granulomatous inflammation of the breast linked to infection with *Corynebacterium* species. However, it has not been fully clarified whether CNGM represents a distinct entity or rather a subtype of IGM [11].

**Figure 1.** Clinical examples of idiopathic granulomatous mastitis.

Treatments strategies including high-dose steroids, immunosuppressive agents, bromocriptine, antibiotics, and surgical resection or even mastectomy have been described in the published cases [10, 12-14]. However, no evidence-based treatment recommendations are available to date.

GRAMAREG will be the first registry for patients with histologically confirmed idiopathic granulomatous mastitis in Europe with an aim to systematically evaluate this uncommon disease and its management as well patient outcomes (duration of symptoms and recurrence rate).

## **4. Methods**

### **4.1. Study design**

Investigator-initiated non-interventional observational international prospective / retrospective cohort study

### **4.2. Aims and objectives**

#### Primary outcomes:

- Proportion of patients presenting with specific symptoms (e.g., pain, redness, palpable mass)
- Duration of symptoms depending on treatment strategy

#### Secondary outcomes:

- Type and duration of systemic treatment
- Number of surgeries, if performed
- Recurrence rate
- Risk factors associated with recurrence
- Time between first symptoms occurring and first histological confirmation
- Presentation on breast imaging (mammography, sonography, MRI, if performed)

The analysis of outcomes regarding diagnostics and ultrasound will be performed by the International Steering Committee GRAMAREG-*sono*.

### **4.3. Inclusion and exclusion criteria**

#### Inclusion criteria

- Histologically confirmed idiopathic granulomatous mastitis or cystic neutrophilic granulomatous mastitis by the local pathology (minimally invasive biopsy or histological confirmation on surgical specimen) after 01.01.2015
- Female / male patients  $\geq 18$  years old
- Signed informed consent form for all patients that are included in the prospective part of the study (presentation with idiopathic granulomatous mastitis after activation of the study at study site)

#### Exclusion criteria

- Patients with suspicion of idiopathic granulomatous mastitis but without histological confirmation
- Suspicion of or confirmed secondary granulomatous mastitis due to e.g., tuberculosis, sarcoidosis, fungal and parasitic infection, foreign body

#### **4.4. Registration**

This study is based on a database with both retrospective and prospective character.

##### **Retrospective data collection:**

Collection and analysis are performed via an anonymized electronic database maintained by EUBREAST e.V. The participating Study Sites commit themselves to identification and documentation of patients with histologically confirmed idiopathic granulomatous mastitis treated during the investigational period at their institution (i.e., between 1st January 2015 and activation of Study Site). No patient identifying information will be disclosed or documented. Data collected during the retrospective phase of the study will be fully anonymous. The retrospective data will not include prospective follow up.

##### **Prospective data collection:**

All patients with histologically confirmed idiopathic granulomatous mastitis presenting at the Study Site after activation of the study will be informed about the possible participation in the GRAMAREG registry. The inclusion and exclusion criteria are verified by the investigator and written informed consent is obtained from the patient.

Diagnostic management and treatment should be conducted according to institutional standards. Since the GRAMAREG study is a non-interventional trial, the Study Sites do not deviate from their own institutional protocol at any timepoint.

[figure not shown]
The follow up on patient status is conducted 1, 3 and 5 years after the first diagnosis. In order to collect follow up data the patients will be contacted directly by the study site to evaluate current symptoms (follow up after 1 year) and to document a potential recurrence of IGM (follow up 1, 3 and 5 years after the first diagnosis).

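### The prospective part is entered on presentation but followed from first diagnosis, so previously diagnosed patients can enter with contacts already past, and recurrence may be biased, probably upwards

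*Protocol*

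**What the plan says.** Section 4.3 (Inclusion criteria) accepts disease confirmed "by the local pathology (minimally invasive biopsy or histological confirmation on surgical specimen) after 01.01.2015". This one date limit covers both parts of the registry. The same section identifies the prospective part as "presentation with idiopathic granulomatous mastitis after activation of the study at study site".

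Section 4.4 (Prospective data collection) uses the same trigger: "All patients with histologically confirmed idiopathic granulomatous mastitis presenting at the Study Site after activation of the study will be informed" about the registry and asked for consent. It then sets the schedule: "The follow up on patient status is conducted 1, 3 and 5 years after the first diagnosis". Current symptoms are evaluated at the 1-year contact only. All three contacts serve "to document a potential recurrence of IGM (follow up 1, 3 and 5 years after the first diagnosis").

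Section 4.4 (Retrospective data collection) covers patients "treated during the investigational period at their institution", from 1 January 2015 to site activation. Those records are anonymous and carry no prospective follow-up.

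The primary outcomes in section 4.2 are the proportion of patients with given presenting symptoms and the duration of symptoms by treatment strategy. Recurrence rate and risk factors for recurrence are secondary. Section 7 limits the analysis to description.

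**The concern.** Entry is tied to one event (presenting after activation) and follow-up to another (first diagnosis). For a newly diagnosed patient the two nearly coincide. For a patient diagnosed earlier they can lie years apart, and nothing in the written criteria keeps such a patient out of the prospective part.

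Three things are then at stake.

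- **Lost contacts.** Contact dates that fall before consent cannot be carried out prospectively, and no analysis plan can recover them.
- **Selection on the outcome.** A previously diagnosed patient typically presents again because disease persisted or came back. Those diagnosed at the same time who stayed well have no occasion to enter. Counting the entrants from first diagnosis is left truncation. It affects recurrence, its risk factors and symptom duration, and it mixes first presentation with later flares in the presenting-symptom outcome.
- **Double counting.** A patient treated before activation who returns afterwards meets the wording of both parts. Because the retrospective records are anonymous, the duplicate cannot be found from the data.

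**Working it through.** The protocol states no sample size, recurrence rate or expected share of previously diagnosed entrants, so there is no figure of its own to reproduce. Two checks apply.

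**1. Dates**

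Inputs from the protocol are the earliest histology (January 2015, section 4.3) and contacts at 1, 3 and 5 years from first diagnosis (section 4.4). Let d be the time from first diagnosis to consent.

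| d | Contacts already past at consent |
|---|---|
| up to 1 year | none |
| more than 1, up to 3 years | year 1 |
| more than 3, up to 5 years | years 1 and 3 |
| more than 5 years | all three |

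This table needs no assumption. To see whether the last row can occur, assume site activation in 2022 to 2025 (the protocol gives no activation dates). The largest possible d at activation is 2022 − 2015 = 7 years, up to 2025 − 2015 = 10 years. All three contacts have passed for anyone diagnosed before about 2022 − 5 = 2017, or 2025 − 5 = 2020 respectively. Anyone with d above 1 year has also lost the only contact at which current symptoms are evaluated.

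**2. Recurrence**

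Let r be recurrence in newly diagnosed patients, f the share of prospective entrants who were diagnosed earlier, and s the proportion of those entrants counted as recurrent. Then

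crude rate = (1 − f) × r + f × s, and bias = f × (s − r).

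All three inputs are assumptions: r = 15-25%, f = 10-30%, and s over its full range.

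| r | f | s = 0 | s = r | s = 50% | s = 100% |
|---|---|---|---|---|---|
| 15% | 10% | 13.5% | 15% | 18.5% | 23.5% |
| 15% | 30% | 10.5% | 15% | 25.5% | 40.5% |
| 25% | 10% | 22.5% | 25% | 27.5% | 32.5% |
| 25% | 30% | 17.5% | 25% | 32.5% | 47.5% |

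For example, the lowest value is 0.70 × 0.15 = 0.105 and the highest is 0.70 × 0.25 + 0.30 × 1 = 0.475. The crude rate therefore spans 10.5-22.5% at s = 0 and 23.5-47.5% at s = 100%.

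The sign of the bias is the sign of s − r. A patient still in an unresolved first episode is not a recurrence and pulls the rate down; one who relapsed pulls it up. Upward bias is the more likely direction, because a known patient who presents again with the disease has either persistent or recurrent disease, and s is then likely to exceed r. That is a judgement; the protocol does not establish it.

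**The case against.** The strongest reply is that the prospective part was meant for new cases. Presentation with the disease can be read as first presentation. The retrospective window closes at activation, so the two parts look designed to meet there, and an earlier patient of the same site would belong to the retrospective part. The 2015 limit is needed for the retrospective part and does not show an intention to enrol old diagnoses prospectively. A clock that starts at first diagnosis suits new cases. A figure between the enrolment text and the follow-up text is not shown; it may be the study flow chart mentioned in the change log, and it could settle the matter.

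This stands to the extent that the protocol does not announce the enrolment of previously diagnosed patients; its wording only permits it. But the criterion does not say first presentation, although the follow-up sentence does specify first diagnosis. The retrospective paragraph does not exclude anyone from the prospective part, least of all a patient treated earlier at another institution. Sites in several countries will apply the written criterion, so it should be clear without a figure.

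A second reply is that an incident flag or delayed entry is material for an analysis plan, which may exist. That is true of the estimation. It is not true of who is enrolled, when the clock starts and what happens to contacts dated before consent, all of which the protocol fixes.

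A third reply concerns direction. A reader might infer that recurrence is inflated as a matter of fact, to some 24-48%. The documents do not support that. The range is a ceiling that counts every previously diagnosed entrant as recurrent, and the same inputs give 10.5-22.5% if none is.

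**Conclusion.** The point holds as a fault in the stated entry rule and time origin. As worded, patients diagnosed as early as 2015 can enter the prospective part on presenting again, some or all of their contacts may precede consent, and a patient can be counted in both parts without detection. Presenting symptoms, symptom duration and recurrence may be biased.

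For recurrence the bias is probably upwards, but neither sign nor size can be estimated from the protocol; it vanishes if s = r and reverses if s is below r. The figures above rest wholly on assumed values of r, f and s. Two further inferences also go too far: that the sponsor intends to enrol previously diagnosed patients, and that some participants will certainly receive no prospective follow-up. Both depend on a reading that the text allows but does not state.

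The change should be made. Part of the damage, the contacts dated before consent, cannot be repaired at analysis.

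**What to change.** In sections 4.3 and 4.4:

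- Define the prospective incident set as patients whose first histological confirmation falls on or after site activation, and use it for presenting symptoms, symptom duration and recurrence.
- State whether previously diagnosed patients may enter the prospective part. If they may, flag them from the date of first histology, and report them separately or analyse them with delayed entry at the consent date.
- State how contact dates that precede consent are handled.
- State which part takes a patient treated before activation who returns afterwards, so that nobody is entered twice.

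The cost is a few sentences and one derived flag. The date of first histology is already needed for the secondary outcome on time from first symptoms to confirmation. The downside is a somewhat smaller main set.

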#### 4.6. Study duration

Open registry due to the rarity of the disease

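### Follow-up symptoms are evaluated only at the 1-year contact, so symptom duration is censored at about 1 year, and later disease unclassifiable, in prospective patients still symptomatic then

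*Protocol*

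**What the plan says.** Protocol section 4.2 lists two primary outcomes. One is the share of patients with particular symptoms at presentation. The other is "Duration of symptoms depending on treatment strategy". Recurrence rate and risk factors for recurrence are secondary outcomes.

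The only text on how follow-up data are obtained is in section 4.4, under prospective data collection. It sets the schedule: "The follow up on patient status is conducted 1, 3 and 5 years after the first diagnosis". It then gives each item its own time points. The stated purpose of the contacts is "to evaluate current symptoms (follow up after 1 year) and to document a potential recurrence of IGM"; a second parenthesis assigns the recurrence item to all three contacts. The text does not mention a date of symptom resolution and defines neither resolution nor recurrence.

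The same section states that retrospective patients have no prospective follow-up. On the course of the disease, section 3 says only that symptoms are mostly severe, "lasting up to many weeks or months". Section 7 limits the analysis to description.

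**The concern.** A duration needs a start and an end. Asking about current symptoms at a single contact gives a status at that time. It does not date the end of the episode. The separate time points for symptoms and for recurrence read as a deliberate distinction, so a site following the text would not ask about symptoms at years 3 and 5.

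Two outcomes are exposed. The first is the primary outcome: the longest episodes are the ones whose end goes unobserved, and information on the long tail is lost although the contacts that could supply it are already scheduled. The second is recurrence: if a patient was symptomatic at year 1 and has disease at year 3, the record does not show whether the first episode ever ended. Section 3 (Rationale) names duration of symptoms and recurrence rate as the patient outcomes the registry is meant to evaluate, so both are central to its purpose.

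**Working it through.** **1. Schedule against outcomes.** The protocol states no sample size, event number or duration estimate, so there is no figure to reproduce. The check is what each contact yields if section 4.4 is followed as written.

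| Contact after diagnosis | Symptoms evaluated | Recurrence documented | Resolution date requested in text |
|---|---|---|---|
| 1 year | yes (current status) | yes | no |
| 3 years | no | yes | no |
| 5 years | no | yes | no |

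**2. What follows for each kind of prospective patient.**

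- Symptomatic at year 1: the duration is known only to exceed the time to that contact. It is right-censored there, and no later observation of its end is planned.
- Free of symptoms at year 1: the episode ended at some time before the contact. Unless a date is recorded elsewhere, the duration is interval-censored.
- Disease reported at year 3 or 5: if the patient was free of symptoms at year 1, this is a recurrence. If the patient was symptomatic at year 1, persistence and recurrence cannot be separated, because no symptom-free interval is established.

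**3. Possible size.** All inputs here are assumptions; none is in the protocol. With median duration m months and Weibull shape k, the share unresolved at 12 months is

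S(12) = exp(−(12/λ)^k), with λ = m/(ln 2)^(1/k), which equals 2^(−(12/m)^k).

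For k = 1 (exponential) this is 2^(−12/m): 2^(−4) = 0.0625, 2^(−2) = 0.25, 2^(−1.33) = 0.397 and 2^(−1) = 0.50.

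| Assumed median | Exponential | Range for k = 0.7 to 1.5 |
|---|---|---|
| 3 months | 6% | 0.4% to 16% |
| 6 months | 25% | 14% to 32% |
| 9 months | 40% | 34% to 43% |
| 12 months | 50% | 50% |

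**4. The clock.** Contacts run from diagnosis, and time from first symptoms to histological confirmation is a separate secondary outcome. If the median is counted from onset and diagnosis comes an assumed 3 months later, the year-1 contact falls 15 months after onset. The exponential share is then 2^(−15/m): 3%, 18%, 31% and 42% for medians of 3, 6, 9 and 12 months. These are shares of all patients from onset. Among those still symptomatic at diagnosis, a constant resolution rate gives back the shares in step 3, since 2^(−15/m) / 2^(−3/m) = 2^(−12/m).

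**The case against.** The strongest objection is that part of the evidence is not visible. The study flow chart mentioned in the change log and the eCRF mentioned in section 5 were not available, and either could hold a resolution date or a symptom item at later contacts. The schedule sentence also speaks of patient status at all three contacts, which is broader than recurrence, and section 5 lets monitors query data that are insufficient for the study aims. This stands as a limit on certainty: the point concerns the protocol text, not the data fields. It does not remove the point, because the sentence that spells out the purpose of the contacts ties symptoms to year 1 alone.

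Stronger readings are tempting, and the documents do not support them:

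- **That the primary outcome has no endpoint.** For patients symptomatic at year 1 it is right-censored. If resolution dates exist for the others and fewer than half are censored, a median can still be estimated.
- **That duration is biased short by a stated amount.** Summarising only resolved patients under exponential medians of 6, 9 and 12 months would give medians of 4.1, 4.7 and 5.0 months, or 32%, 48% and 58% too short. That assumes an analysis of completed durations alone, which the protocol nowhere states, and a 12-month clock from onset. A Kaplan-Meier median would also count as descriptive.
- **That patients not yet at year 1 distort every data cut.** Section 4.6 describes an "Open registry due to the rarity of the disease", but how incomplete follow-up is handled belongs to an analysis plan.
- **That no later disease can be told from recurrence.** The ambiguity is confined to patients symptomatic at year 1, and they are identifiable.
- **That strategies used in the worst cases suffer most.** Nothing in the document shows how severity relates to treatment strategy.

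The retrospective part may contain charted courses longer than a year. It gets no prospective follow-up, so it cannot supply the missing end dates of prospective patients.

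**Conclusion.** The point holds for prospective patients still symptomatic at the 1-year contact. As section 4.4 is written, their symptom duration is right-censored at about 1 year after diagnosis, and disease reported at years 3 or 5 cannot be classed as persistence or recurrence. A primary outcome and the recurrence rate are both affected. It is a matter for the protocol because it concerns which data are collected; no later analysis can recover dates that were never requested.

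The size is unknown. On the assumed exponential medians of 3 to 12 months, the affected share runs from about 6% to 50%, and it is lower if the median is counted from onset for all patients. The gap is minor if most episodes resolve within a few months and substantial if many last nine months or more; the protocol's description of the course does not decide between these. The conclusion assumes that the flow chart and eCRF do not already fill the gap.

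**What to change.** Amend the follow-up paragraph in Protocol section 4.4, and the flow chart and eCRF where they do not already do this, so that the 1-, 3- and 5-year contacts each record:

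- symptoms present, yes or no;
- month and year of symptom resolution, if resolved;
- if disease is present, whether there was a symptom-free interval since the first episode (recurrence) or none (persistence).

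State in the same place what counts as resolution and as recurrence for recording purposes. How censored durations are summarised can be left to the analysis plan.

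The cost is a protocol wording change and a few extra questions at contacts already scheduled. The downside is that recalled dates, especially at years 3 and 5, will be approximate.

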#### **4.5. Target accrual**

Unlimited

#### 4.6. Study duration

Open registry due to the rarity of the disease

## 5. Data management

This part of the Protocol will discuss the Data Sharing and Data Management policy between two parties: The Provider & The Recipient. The Provider as per this agreement will be the Study Site supplying the dataset in accordance with the Protocol of the study. The Recipient will be EUBREAST e.V. who will collect the data in accordance with the Data Protection policy as set out in this agreement. Study data will be collected and managed using REDCap (Research Electronic Data Capture) electronic data capture tools hosted at the server belonging to and managed by EUBREAST.

To register for the study, Study Sites (Providers) will contact the Head of their National Steering Committee to request participation in the Study and access to the online database. Each Study Site will then be designated a Site ID in format: Two-letter Country Code – Site number (e.g., DE-001 for the first German Study Site), which will be used as a prefix for the Patient ID (e.g., DE-001-001 for the first patient recruited at Study Site DE-001). All patients who consent to participation in the Study are recorded in the Subject Identification Log that remains at the study site. This document is the only record containing patient personal data and the corresponding Patient ID. EUBREAST does not have access to the Subject Identification Log at any time. No personal data will be disclosed under the Data Sharing Agreement. No patient identifiable data will be recorded for the purpose of the Study.

For further analysis data are filled in the REDCap-based eCRF by the Study Site. The printed version of CRF (PDF file) is also available. Its use is optional. All data are checked for plausibility through remote monitoring. The Monitors do not have access to patient data and do not visit Study Sites. Are the data insufficient for evaluation of predefined study aims, the Monitor will generate a query and Study Site will be requested to clarify.

REDCap has been disseminated for local use by more than 1,005 academic/non-profit consortium partners in 79 countries. Vanderbilt leads the REDCap Consortium, which currently supports more than 99,000 projects and 128,000 users. More information about the consortium and system security can be found at <http://www.projectredcap.org/>. REDCap is a secure, web-based application designed to support data capture for research studies, providing 1) an intuitive interface for validated data entry; 2) audit trails for tracking data manipulation and export procedures; 3) automated export procedures for seamless data downloads to common statistical packages; and 4) procedures for importing data from external sources.

REDCap is created by Vanderbilt University, with the server hosted by the EUBREAST. REDCap was developed specifically around HIPAA-Security guidelines. Web browser communication to the server is SSL-encrypted by default. All other ports are firewall protected. Data is stored in MySQL databases on a separate server. This server is behind a firewall and can only be accessed from the IP address of the web server. An SSL-tunnel encrypts communication between the web and databases servers. File upload is secured between servers using the WebDAV protocol with SSL. “At rest” encryption is in place on the database server (aes-xts-plain64:sha256 with 512-bit keys). Daily back-ups are made of both servers and stored for two weeks prior to being deleted. Operating security updates are installed automatically. Antivirus software runs to a scheduled protocol on the web server. User passwords are managed directly. Accounts are disabled after 5 failed login attempts. Users are auto logged out after 30 mins of no activity. Daily audit tracking of users is in place with removal of unused user accounts.

